6.3.11 Deaths

All deaths that occur during the study, or within the protocol defined 30 day post study follow up period after the administration of the last dose of study treatment, must be reported as follows:

- Death clearly the result of disease progression should be reported to the study monitor at the next monitoring visit and should be documented in the eCRF but should not be reported as an SAE.
- Where death is not due (or not clearly due) to progression of the disease under study, the AE causing the death must be reported to the study monitor as a SAE within 24 hours (see Section 6.3.8 for further details). The report should contain a comment regarding the co involvement of progression of disease, if appropriate, and should assign main and contributory causes of death. This information can be captured in the 'death eCRF'.
- Deaths with an unknown cause should always be reported as a SAE. A post mortem maybe helpful in the assessment of the cause of death, and if performed a copy of the post-mortem results should be forwarded to AstraZeneca within the usual timeframes.

6.4 Reporting of serious adverse events

Investigators and other site personnel must inform the KFDA, via a MedWatch/AdEERs form, of any serious or unexpected adverse events that occur in accordance with the reporting obligations of 21 CFR 312.32, and will concurrently forward all such reports to AZ. A copy of the MedWatch/AdEERs report must be faxed to AstraZeneca at the time the event is reported to the KFDA. It is the responsibility of the investigator to compile all necessary information and ensure that the KFDA receives a report according to the KFDA reporting requirement timelines and to ensure that these reports are also submitted to AstraZeneca at the same time.

* A cover page should accompany the MedWatch/AdEERs form indicating the following:

- Investigator Sponsored Study (ISS)
- The investigator IND number assigned by the KFDA
- The investigator's name and address
- The trial name/title and AstraZeneca ISS reference number

* Investigative site must also indicate, either in the SAE report or the cover page, the causality of events in relation to all study medications and if the SAE is related to disease progression, as determined by the principal investigator.

* Send SAE report and accompanying cover page by way of fax to AstraZeneca's designated fax line:

If a non-serious AE becomes serious, this and other relevant follow-up information must also be provided to AstraZeneca and the KFDA.

Serious adverse events that do not require expedited reporting to the KFDA need to be reported to AstraZeneca preferably using the MedDRA coding language for serious adverse events. This information should be reported on a monthly basis and under no circumstance less frequently than quarterly.

For all studies of AZD9291, the Sponsor should continue sending SUSARs to AZ in parallel to regulatory authorities as defined per AZ standard minimum requirements for safety data collection; all other SAEs should be sent to AZ on a monthly basis.

In the case of blinded trials, AstraZeneca will request that the Sponsor either provide a copy of the randomization code/ code break information or unblind those SAEs which require expedited reporting.

All SAEs have to be reported to AstraZeneca, whether or not considered causally related to the investigational product. All SAEs will be documented. The investigator is responsible for informing the IRB and/or the Regulatory Authority of the SAE as per local requirements.

Non-serious adverse events and SAEs will be collected from the time consent is given, throughout the treatment period and up to and including the 30 day follow-up period. After withdrawal from treatment, subjects must be followed-up for all existing and new AEs for 30 calendar days after the last dose of trial drug and/or until event resolution. All new AEs occurring during that period must be recorded (if SAEs, then they must be reported to the FDA and AstraZeneca). All study-related toxicities/ SAEs must be followed until resolution, unless in the Investigator's opinion, the condition

is unlikely to resolve due to the patient's underlying disease.

6.5 Overdose

There is no specific treatment in the event of AZD9291 overdose, and symptoms of overdose are not established. In the event of an overdose, physicians should follow general supportive measures and should treat symptomatically.

For overdoses associated with a SAE, the standard agreed reporting timelines apply, see Section 6.3.8.

6.6 Pregnancy

All pregnancies and outcomes of pregnancy should be reported to AstraZeneca.

6.6.1 Maternal exposure

If a subject becomes pregnant during the course of the study AZD9291 should be discontinued immediately. Pregnancy itself is not regarded as an adverse event unless there is a suspicion that the investigational product under study may have interfered with the effectiveness of a contraceptive medication. Congenital abnormalities/birth defects and spontaneous miscarriages should be reported and handled as SAEs. Elective abortions without complications should not be handled as AEs. The outcome of all pregnancies (spontaneous miscarriage, elective termination, ectopic pregnancy, normal birth or congenital abnormality) should be followed up and documented even if the subject was discontinued from the study. If any pregnancy occurs in the course of the study, then the Investigator or other site personnel informs the appropriate AstraZeneca representatives within 1 day i.e., immediately but no later than 24 hours of when he or she becomes aware of it. The designated AstraZeneca representative works with the Investigator to ensure that all relevant information is provided to the AstraZeneca Patient Safety data entry site within 1 or 5 calendar days for SAEs and within 30 days for all other pregnancies.

The same timelines apply when outcome information is available.

6.6.2 Paternal exposure

Pregnancy of the subject's partners is not considered to be an adverse event. However, the outcome of all pregnancies (spontaneous miscarriage, elective termination, ectopic pregnancy, normal birth or congenital abnormality) should if possible be followed up and documented. To capture information about a pregnancy from the partner of a male subject, the male subject's partner consent must be obtained to collect information related to the pregnancy and outcome; the male subject should not be asked to provide this information. A consent form specific to this situation must be used. The outcome of any conception occurring from the date of the first dose until 6 months after dosing ends should be followed up and documented.

6.7 Management of IP related toxicities

Dose adjustment for adverse events should be in accordance with the following table:

Table 3. AZD9291 dose adjustment information for adverse reactions

Target Organ	Adverse Reactiona	Dose Modification
Pulmonary	ILD/Pneumonitis	Permanently discontinue AZD9291
Cardiac	QTc interval greater than 500 msec on at least 2 separate ECGs	Withhold AZD9291 until QTc interval is less than 481 msec or recovery to baseline if baseline QTc is greater than or equal to 481 msec, then restart at a reduced dose (40 mg). QTc interval prolongation with signs/symptoms of serious arrhythmia Permanently discontinue AZD9291
Other	Grade 3 or higher adverse reaction	Withhold AZD9291 for up to 3 weeks If Grade 3 or higher adverse reaction improves to Grade 0-2 after withholding of AZD9291 for up to 3 weeks AZD9291 may be restarted at the same dose (80 mg) or a lower dose (40 mg) Grade 3 or higher adverse reaction that does not improve to Grade 0-2 after withholding for up to 3 weeks Permanently discontinue AZD9291

a Note: The intensity of clinical adverse events graded by the National Cancer Institute (NCI) Common Terminology Criteria for Adverse Events (CTCAE) version 4.0.

If a patient experiences a CTCAE grade 3 or higher and/or unacceptable toxicity (any grade), where the clinician considers the event of concern to be specifically associated with AZD9291 (and not attributable to the disease or disease-related processes for which patient is being treated), dosing will be interrupted and supportive therapy administered as required in accordance with local practice/guidelines. Detailed information on the clinical management of events may be found in Appendix B, "Guidance for the Management of Adverse Events in Studies using 80mg AZD9291."

Patients with QTc prolongation (i.e., confirmed QTc prolongation to >500 msec absolute or a > 60

msec increase from baseline) should have AZD9291 treatment interrupted and regular ECGs performed until resolution to baseline.

If the toxicity resolves or reverts to \leq CTCAE grade 2 within 3 weeks of onset, treatment with AZD9291 may be restarted at the same dose (80 mg, daily) or a lower dose (40 mg, daily) using the rules below for dose modifications (Table 4). There will be no individual modifications to dosing schedule in response to toxicity, only potential dose reduction or dose interruption.

If the toxicity does not resolve to \leq CTCAE grade 2 after 3 weeks, then the patient should be withdrawn from the study and observed until resolution of the toxicity.

Table 4. Dose Interventions

Intervention	AZD9291 Dose
Starting Dose	80 mg daily
Reduced Dose	40 mg daily

On resolution of toxicity within 3 weeks:

If an event subsequently requires dose interruption, AZD9291 may restart at the same dose or the reduced dose, on resolution/improvement of the event at the discretion of the clinician.

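### After a hold for QTc above 500 msec, Table 3 directs restart at 40 mg, but the section 6.7 restart paragraph allows 80 mg or 40 mg with no QTc exception

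*Combined protocol and SAP*

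**What the plan says.** Section 6.7 opens by sending the reader to Table 3: "Dose adjustment for adverse events should be in accordance with the following table". The Cardiac row of that table has the trigger "QTc interval greater than 500 msec on at least 2 separate ECGs". Its instruction is "Withhold AZD9291 until QTc interval is less than 481 msec" (or back to baseline, where baseline is 481 msec or more), "then restart at a reduced dose (40 mg"). A second cardiac entry permanently stops patients whose QTc prolongation comes with signs or symptoms of serious arrhythmia. The Other row covers grade 3 or higher reactions that improve to grade 0-2 within 3 weeks, and it gives a choice: "AZD9291 may be restarted at the same dose (80 mg) or a lower dose (40 mg").

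Three paragraphs of running text follow the table:

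- The first interrupts dosing for drug-related grade 3 or higher events, or for unacceptable toxicity of any grade, and cites Appendix B for detail.
- The second says that patients with confirmed QTc above 500 msec, or a rise of more than 60 msec, "should have AZD9291 treatment interrupted and regular ECGs performed until resolution to baseline".
- The third covers a toxicity that has resolved or improved to grade 2 or lower no more than 3 weeks after it began. Its rule is this: "treatment with AZD9291 may be restarted at the same dose (80 mg, daily) or a lower dose (40 mg, daily"). It points to Table 4 for how to modify the dose.

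Table 4 lists a starting dose of 80 mg and a reduced dose of 40 mg, without conditions. The sentence beneath it reads "If an event subsequently requires dose interruption, AZD9291 may restart at the same dose or the reduced dose", at the clinician's discretion.

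Section 6.7.2 restates the QTc hold and adds a 3-week stopping rule. Section 7.2 refers back to 6.7 for when the dose may be reduced, and bars re-escalation after a reduction.

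**The concern.** Table 3 names one dose for restart after QTc above 500 msec. The restart paragraph offers two, and it comes straight after the paragraph on holding for QTc. A site working down the page from the QTc hold reaches a sentence about the toxicity that permits 80 mg, and nothing there sends it back to the Cardiac row.

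What is at stake is patient safety at restart. A patient whose QTc exceeded 500 msec on 80 mg could go back to that same dose. The extra ECGs are required only until QTc is back to baseline. After that, section 5.2.3 asks for an ECG every cycle, and the synopsis puts visits 4 weeks apart after the first cycle. The plan has approximately 10 sites, and they should all apply one rule.

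**Working it through.** No figure in the plan needs reproducing. The check is a comparison of the rules for one event, a hold for QTc above 500 msec on at least 2 separate ECGs.

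| Place | Applies to | Restart dose |
|---|---|---|
| Table 3, Cardiac row | This event, by name | 40 mg |
| Table 3, Other row | Grade 3 or higher reactions not in a named row | 80 mg or 40 mg |
| 6.7, QTc hold paragraph | Confirmed QTc above 500 msec, or a rise above 60 msec | None given |
| 6.7, restart paragraph | The toxicity, type not specified | 80 mg or 40 mg |
| 6.7, sentence after Table 4 | An event that subsequently needs interruption | Same or reduced dose |
| 7.2 | Any reduction | Refers to 6.7 |

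1. **Isolate the dose question.** Take a patient on 80 mg with QTc above 500 msec on two separate ECGs and no sign of serious arrhythmia, whose QTc is back at baseline within 3 weeks of onset. A baseline below 481 msec meets the main recovery condition in Table 3, and a higher one meets its alternative. The event has also resolved in the sense of the restart paragraph. Only the restart dose is then open.

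2. **Apply each rule.** Table 3 gives 40 mg. The restart paragraph, if it covers this patient, gives 80 mg or 40 mg. The rules differ on whether 80 mg is allowed.

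3. **Does the restart paragraph cover this patient?** Its subject is the toxicity, with no restriction by type, and the event described immediately before it is the QTc hold. Section 6.7.2 uses the same term for QTc prolongation, so the term does not exclude QTc events elsewhere in the document. Nothing in the paragraph confines it to the Other row.

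4. **Is the conflict settled elsewhere?** Section 7.2 points back to 6.7, and Table 4 lists both doses without conditions. The sentence after Table 4 is weaker support, because it concerns an event that subsequently requires interruption. Still, it has no QTc exception either.

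5. **Size.** The dose ratio is 80/40 = 2. A patient already on 40 mg is not exposed to the discrepancy, because section 7.2 bars re-escalation.

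6. **Outside the point.** Holds triggered only by a rise of more than 60 msec have no QTc row in Table 3, so there is no directed dose to conflict with. Patients with signs or symptoms of serious arrhythmia are permanently stopped.

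**The case against.** The best defence is that the structure of 6.7 already resolves this. The opening line makes Table 3 the rule, the Cardiac row is specific and directive, and the restart paragraph is general and permissive. Restarting at 40 mg satisfies every sentence. The restart paragraph also tracks the Other row closely: the same improvement to grade 2 or lower, the same 3 weeks, the same choice of doses. Its reference to the toxicity can look back past the QTc paragraph to the one before it, which does use that word. The QTc paragraph does not use it, and names baseline where the restart paragraph names grade 2.

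Much of this stands. It makes Table 3 the likelier intention, and the plan does not instruct anyone to give 80 mg. But the opening line does not say what happens when text under the table is more permissive, and the restart paragraph is not tied to the Other row. The right dose has to be inferred.

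Two limits on the evidence also stand. Appendix B, cited for managing events, was not available and may address restart after QTc prolongation. The lead-in under Table 4 about resolution within 3 weeks is followed at once by the sentence on a subsequent interruption, so a line may have been lost when the text was extracted. Neither would make the unqualified restart paragraph clear as it stands.

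A reader might go further in two ways that the documents do not support:

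- **That 6.7.2 contradicts Table 3.** It gives no restart dose, but that is an omission. It need not repeat a dose already in the table.
- **That the plan sets incompatible QTc recovery limits with a measurable gap**, since Table 3 uses below 481 msec and the text speaks of baseline. The reference to baseline may limit only how long the regular ECGs continue, in which case dosing could resume below 481 msec while ECGs go on. A gap in msec would also require baseline to equal the screening value. No size can be put on it.

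**Conclusion.** The point holds as a dosing-safety conflict in wording. Table 3 directs 40 mg after QTc above 500 msec on at least 2 separate ECGs. The restart paragraph, read where it stands, permits 80 mg for the same event. The size is a two-fold difference in daily dose, confined to patients on 80 mg at the time of the hold. How many patients that would be is unknown, because the documents give no event rate and none is assumed here.

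The conclusion rests on two readings: that the restart paragraph can reasonably be taken to include QTc events, and that confirmed prolongation above 500 msec in the text is the same event as the Table 3 trigger. Confidence is moderate, because the opening line of 6.7 favours Table 3 and Appendix B could not be checked.

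A reader might infer that the trial's result is affected. It is not: the two-stage design, the sample size and the response-rate analysis do not depend on this rule.

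**What to change.** Add to the restart paragraph in section 6.7, and to the sentence after Table 4: *except after QTc >500 msec on at least 2 separate ECGs, where the Cardiac row of Table 3 applies and AZD9291 restarts at 40 mg only*. In section 6.7.2, add a cross-reference to that row. Check Appendix B at the same time, so that it gives the same restart dose if it gives one.

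The cost is one clause in two places and one cross-reference, made by protocol amendment. It needs no extra visits, procedures or patients, and no change to the analysis.

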Clinical Study Protocol

Drug Substance AZD9291 (Osimertinib)

Study Code ESR-16-12348

Edition Number 1

Date 19 Jan, 2017

Phase II study of osimertinib in NSCLC patients with EGFR exon 20 insertion mutation

Sponsor: [name], Seoul National University Hospital, Seoul, Korea

The following Amendment(s) and Administrative Changes have been made to this protocol since the date of preparation:

PROTOCOL SYNOPSIS

Phase II study of osimertinib in NSCLC patients with EGFR exon 20 insertion mutation

National Co-ordinating Investigator

[name], Associate Professor

Department of Internal Medicine

Seoul National University Hospital

[name]

Study site(s) and number of subjects planned

This study will be conducted at approximately 10 sites in South Korea with approximately 30 patients enrolled and dosed and at least 27 evaluable patients required (evaluable for the primary analysis). All patients will be recruited from South Korea.

Study period	Phase of development
Estimated date of first subject enrolled	Q2 2017
Estimated date of last subject completed	Q2 2019

Study design

This is a single-arm, non-randomized multicentre phase 2 study in NSCLC patients with EGFR exon 20 insertion mutation, whose disease has progressed on standard chemotherapy. Patients will have bi-weekly clinic visits for the first 4 weeks (1st cycle); thereafter visits will be every 4 weeks. Safety and efficacy assessments will be collected. Patients' medical care will be performed according to local clinical practice.

Objectives

Primary Objective Outcome Measure

To determine the efficacy of osimertinib in patients with advanced or metastatic NSCLC with EGFR exon 20 insertion mutation who show disease progression on standard chemotherapy.
Investigator-assessed objective response as defined by RECIST version 1.1

Secondary Objectives Outcome Measure

To evaluate the safety and tolerability of osimertinib AEs/SAEs as defined by NCI CTCAE version 4.0

To evaluate progression-free survival (PFS) PFS as defined by RECIST version 1.1

To evaluate overall survival (OS)

To evaluate the efficacy based on subtypes of EGFR exon 20 insertion mutation

To evaluate PFS based on subtypes of EGFR exon 20 insertion mutation

Target subject population

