1.4 Study Design

This is a single-arm, non-randomized multicentre phase 2 study in NSCLC patients with EGFR exon 20 insertion mutation, whose disease has progressed on standard chemotherapy. Full details of the assessments conducted at each visits are shown in Table 1.

Figure 1 Study flow chart

(a) Patients will continue to receive osimertinib until objective disease progression (according to RECIST 1.1) or for as long as they are receiving clinical benefit in the opinion of the Investigator unless any of the criteria for treatment discontinuation are met first. Patients who discontinue study treatment for reasons other than disease progression must continue tumour assessments as per the protocol schedule until progression.

2. Study objectives

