3.9.1 Procedures for discontinuation of a subject from investigational product

At any time, subjects are free to discontinue investigational product or withdraw from the study (i.e., investigational product and assessments – see Section 0), without prejudice to further treatment. A subject that decides to discontinue investigational will always be asked about the reason(s) and the

presence of any adverse events. If possible, they will be seen and assessed by an Investigator(s). Adverse events will be followed up (See Section 0); and all study drugs should be returned by the subject. If a subject is withdrawn from study, see Section 0.

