3.10.2 Withdrawal of the informed consent

Patients are free to withdraw from the study at any time (investigational product and assessments), without prejudice to further treatment. A patient who withdraws consent will always be asked about the reason(s) and the presence of any adverse events (AE). The investigator will follow up AEs outside of the clinical study. If a subject withdraws from participation in the study, then his/her enrolment code cannot be reused. Withdrawn subjects will be replaced.

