5.1 Efficacy assessments

RECIST 1.1 guidelines for measurable, non-measurable, target lesions (TLs) and non-target lesions (NTLs) and the objective tumour response criteria are present. Baseline CT or MRI assessments of chest and abdomen (including liver and adrenal glands) must be performed no more than 28 days before the start of study treatment, and ideally should be performed as close as possible to the start of study treatment. Additional imaging may be performed based on individual patient signs and symptoms. The methods of assessment used at baseline should be used at each subsequent follow-up assessment. Follow-up assessments should be performed every 2 cycles (\pm 7 days) after the start of treatment until objective disease progression as defined by RECIST 1.1. Any other sites at which new disease is suspected should also be appropriately imaged. If an unscheduled assessment is performed and the patient has not progressed, every attempt should be made to perform subsequent assessments at the scheduled visits whilst the patient remains on study treatment.

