6.7.2 QTc Prolongation

Patients with QTcF prolongation fulfilling the following criteria (i.e., confirmed QTcF prolongation to > 500 msec absolute or a > 60 msec increase from baseline) should have AZD9291 interrupted and regular ECGs performed until resolution to baseline. If the toxicity does not resolve to < grade 1 within 3 weeks the patient will be permanently withdrawn from AZD9291 treatment.

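### Section 6.7 takes patients with unresolved Grade 3 or higher toxicity out of the study where Table 3 only stops the drug, so required tumour scans could be lost

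*Combined protocol and SAP*

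**What the plan says.** Section 6.7 gives two instructions for the same event, a Grade 3 or higher toxicity that has not come down to Grade 2 or below after 3 weeks.

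- The row in Table 3 reads "Grade 3 or higher adverse reaction that does not improve to Grade 0-2 after withholding for up to 3 weeks Permanently discontinue AZD9291".
- The text after the table says "then the patient should be withdrawn from the study and observed until resolution of the toxicity".

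The neighbouring 3-week rule for QTc prolongation in section 6.7.2 is worded like Table 3: "the patient will be permanently withdrawn from AZD9291 treatment".

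Two other places govern tumour assessment once the drug has stopped. Note (a) to Figure 1 in section 1.4 states: "Patients who discontinue study treatment for reasons other than disease progression must continue tumour assessments as per the protocol schedule until progression". Section 5.1 schedules scans every 2 cycles "after the start of treatment until objective disease progression as defined by RECIST 1.1", so the schedule ends at progression and not at the last dose.

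The protocol indicates what leaving the study means in two places. Section 3.9.1 refers to a subject's freedom to "withdraw from the study (i.e., investigational product and assessments", and section 3.10.2 says "Patients are free to withdraw from the study at any time (investigational product and assessments".

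**The concern.** Stopping the drug and leaving the study are different acts in this protocol. The first keeps the patient on the scan schedule. The second, as sections 3.9.1 and 3.10.2 describe it, ends assessments too. If the section 6.7 sentence is taken at its word, a patient with unresolved toxicity and no progression comes off the scan schedule, and the only follow-up that sentence names is of the toxicity.

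PFS, a secondary endpoint, is the most exposed. Follow-up would end because of a treatment effect, so the censoring may be informative. For example, if patients taken off the drug progress sooner than those who stay on it, dropping their later scans would make the Kaplan-Meier curve look too favourable. Section 8.5.2 gives no PFS censoring rule, so the date at which such a patient would be censored is not known either.

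The primary endpoint is less exposed. A response already recorded is safe, and one could be missed only if none had been recorded before withdrawal. A patient withdrawn before the first on-treatment scan stays in the efficacy set, because section 8.3 asks only for dosing and a baseline tumour assessment, but would have no response assessment.

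**Working it through.** **The design figure, for reference.** The sample size in section 8.2 reproduces and does not depend on this wording. The rule is at least 1 response in 13, then at least 4 in 27. The probability of success is the sum over x ≥ 1 of P(X₁ = x) × P(X₂ ≥ 4 − x), with X₁ binomial on 13 patients and X₂ binomial on 14.

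- At a response rate of 0.05 this gives 0.0416, within the 5% limit.
- At 0.20 it gives 0.801, against the stated 80%.
- Enrolment: 27 / (1 − 0.10) = 30.

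**Step 1: the two rules side by side.**

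| Source | Event | Action |
|---|---|---|
| Table 3, section 6.7 | Grade 3+ not improved to Grade 0–2 after up to 3 weeks of withholding | Stop the drug for good |
| Text of section 6.7 | Toxicity not resolved to Grade 2 or below after 3 weeks | Leave the study; toxicity observed |
| Section 6.7.2 (QTc) | Not resolved within 3 weeks | Stop the drug for good |

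The first two rows describe the same event with different actions. The third shows the protocol using drug-only wording for a closely similar rule.

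**Step 2: what study withdrawal implies.** Sections 3.9.1 and 3.10.2 both attach product and assessments to it. Both concern a subject's own choice, so carrying that meaning to section 6.7 is an inference. No other passage says what study withdrawal means for a treated patient's assessments.

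**Step 3: conflict with the scan rules.** A patient stopped for toxicity has stopped for a reason other than progression, which is the case note (a) covers, and scanning is mandatory there. Section 5.1 also runs scans to progression. One phrase in section 5.1 is limited to patients still on treatment, but it concerns returning to schedule after an unscheduled scan. It does not end scanning when the drug stops.

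**Step 4: when the first scan would be missed.** Inputs:

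- Cycle length is 4 weeks, from the synopsis: "Patients will have bi-weekly clinic visits for the first 4 weeks (1st cycle); thereafter visits will be every 4 weeks".
- Scans are every 2 cycles, ± 7 days (section 5.1).
- The recovery period is 3 weeks, or 21 days (section 6.7).
- Assumption: the drug is withheld from the day of onset.

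First scan: 2 × 4 weeks = 8 weeks = Day 56, with a window from 56 − 7 = Day 49 to 56 + 7 = Day 63.

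Withdrawal day = onset day + 21. It falls before the first scan when onset is earlier than:

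- 56 − 21 = Day 35 for a scan on its due date;
- 49 − 21 = Day 28 for the earliest scan in the window;
- 63 − 21 = Day 42 for the latest.

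With later onset at least one scheduled scan comes before withdrawal, and only subsequent scans are at risk.

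**Step 5: how many patients.** No rate for toxicity unresolved at 3 weeks is given, so no expected count is computed. One patient is 1/27 = 3.7% of the evaluable target, or 1/30 = 3.3% of planned enrolment.

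**The case against.** The strongest reply is that the protocol already settles the matter. Section 6.7 opens by making Table 3 the rule for dose adjustment. Note (a) deals with exactly this patient and is mandatory, while the section 6.7 sentence is only a recommendation and does not mention scans. Section 3.9 lists an adverse event as a reason to discontinue osimertinib, and section 3.10 confines withdrawal to screen failure and withdrawn consent, so toxicity belongs with drug discontinuation. The sentence also keeps the patient under observation, which fits poorly with stopping all assessments. Harm needs a chain: a Grade 3 or higher toxicity, unresolved at 3 weeks, in a patient without progression, at a site that follows this sentence over note (a) and section 5.1.

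Much of this stands. The weight of the protocol favours drug discontinuation, toxicity follow-up is preserved (section 6.4 also keeps it), PFS is descriptive, and the chain may rarely be completed. But these points show that the section 6.7 sentence is the wrong one; they do not remove it. Staff handling an unresolved Grade 3 event will be reading section 6.7, and about 10 sites could resolve the contradiction differently. Appendix B, cited there for detailed management, is not in the text available, so it cannot be said whether it helps.

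**Conclusion.** The concern holds. Section 6.7 contradicts its own Table 3, and read literally it conflicts with the scan requirements in note (a) to Figure 1 and section 5.1. It should be fixed, but it does not undermine the design: the two-stage rule and sample size are unaffected.

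The textual mismatch is certain. Two things are less so. That scans would stop rests on reading study withdrawal as sections 3.9.1 and 3.10.2 use it. The extent of any loss cannot be calculated without an event rate. What can be stated is that onset before about Day 35 (Day 28 to Day 42 across the window) would leave a patient without any scheduled on-treatment scan, assuming the drug is withheld from onset. If withholding starts later and the 3 weeks run from that point, as Table 3 implies, the cut-off for onset moves earlier by the length of the delay.

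**What to change.** In the text of section 6.7, change the instruction for toxicity unresolved after 3 weeks so that the patient is *permanently discontinued from AZD9291*, matching Table 3 and section 6.7.2. Keep the requirement to observe the toxicity until it resolves. Add one sentence: *Tumour assessments continue on schedule until progression (Figure 1, note (a)).*

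The cost is one phrase and one added sentence, which can go into the next amendment. It requires no scan beyond those that section 1.4 and section 5.1 already demand.
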